## Statistical Analysis Plan

All subjects who completed the study were included in the analysis. Summary statistics were expressed in mean  $\pm$  S.D. for continuous variables, and counts (percentage %) for categorical variables. Differences between treatment groups were tested using Student's *t*-test. Two-sample Wilcoxon test is used when variables appear to violate distributional assumptions. Model assumptions were assessed within an ANCOVA model predicting 12 week outcome, adjusting for baseline. Fisher's exact test or chi-square test was performed for categorical variables. An  $\alpha$  level of  $p < 0.05$  was considered statistically significant. Statistical analysis was conducted in R 3.4 (R Core Team 2017, Vienna Austria).

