 - HIV or AIDS based on self-report.
 - Steroid use with the exception of over-the-counter topical and nasal steroids such as Flonase.
 - Allergy medication or regular antihistamine use.

- Seizure disorders. Acceptable if managed with medication and free of seizure activity for 5 years.
 - Smoking or the use of nicotine replacement products in the past 6 months.
 - Use of dietary supplements containing vitamins (except Calcium and Vitamin D), minerals, herbal or plant-based preparations, fish oil or homeopathic remedies during study participation unless willing to discontinue prior to enrollment.
 - Current participation in another research study.
 - Non-English speaking.
 - No social security number.
 - Participation in another research study.
- **Withdrawal/Termination Criteria:** Low compliance including taking less than 80% of study supplements, or missing study visits. Subjects who manifest an allergic reaction to the study supplement or placebo. Negative health effects as determined by the study physician. In the event of a withdrawal/termination, study subjects will be asked to discontinue their study supplement, and, if necessary due to negative health effects, will be referred to their primary care physician.

*Note: Screening lab values that would interfere with study outcomes are determined at the discretion of the study physician.

D. Risk/Benefit Assessment: We do not anticipate any major risks or hazards to participants in this study.

There are no benefits to participation in this study. EMIQ has been independently evaluated by an expert panel as safe and has been categorized as GRAS (generally recognized as safe) according to the Food and Drug Administration (FDA)(see attachment “5. FDA GRAS EMIQ”). Other investigators have conducted similar clinical studies with EMIQ at doses comparable to those in this study and reported no adverse effect.

While all measures to ensure confidentiality will be taken, it is an ever present possibility that it may be lost. Stored samples will be labeled with a unique number (code) that will not contain any private information such as name or date of birth to ensure the samples cannot be identified. There is no intention for allowing anyone other than the principal investigator to have access to these codes. If [name] turns this study over to a new principal investigator, he will give the key code to the new principal investigator.

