Visit 2, Baseline: A 10mL (2 teaspoons) blood sample will be drawn into red marble top tubes for liver and kidney function tests, insulin and adiponectin. An additional 7mL (1.4 teaspoons) of blood will be drawn into lavender top tubes for analysis of lipids. A spot urine sample will be provided for urinalysis.

Visit 3, Week 4: A 5mL (1 teaspoon) blood sample will be drawn into a gold topped tube for liver/kidney function testing.

Visit 4, Week 8: A 5mL (1 teaspoon) blood sample will be drawn into a gold topped tube for liver/kidney function testing.

Visit 5, Final: A 3mL (0.6 teaspoons) blood sample will be drawn into a lavender topped tube for CBC differential analysis. A 10mL (2 teaspoons) blood sample will be drawn into red marble top tubes for liver and kidney function tests, insulin and adiponectin. An additional 7mL (1.4 teaspoons) of blood will be drawn into lavender top tubes for analysis of lipids. A spot urine sample will be provided for urinalysis.

*Note: Visits 3 and 4 will be used to monitor participant's liver and kidney function during the study. If the study physician determines that liver function appears to be in jeopardy, subjects will be asked to discontinue the supplement and to take medical action at the discretion of the study physician.

*Note: Abnormal lab values found at screening will be provided to the volunteers in writing. Abnormal values for safety labs (those falling outside of the study physician's predetermined range) will be repeated. The study physician will be notified and determine any follow-up action.

Nutritional Intake and Physical Activity:

Subjects will receive a Food Amount Booklet and information about the 24-hour recalls at visit 1. The Dietary Assessment Unit will collect three (3) 24-hour recalls by phone (two weekdays and a weekend) between visits 1 and 2. Three recalls will be collected by phone again between visits 3 and 4 (around week 6, midway through the 12 week supplementation period) and between visits 4 and 5 (around weeks 11-12). Dietary intake data will be analyzed using Nutrition Data System for Research software version 2015, developed by the Nutrition Coordinating Center (NCC), University of Minnesota, Minneapolis, MN.

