Volunteers will be asked **not to change** their regular physical activity; unless, their total physical activity per week amounts to greater than 150 minutes, in which case they will be asked to refrain from exercise 30 days prior to participating in the study and to continue refraining from exercise until the end of the study. In addition, volunteers will be subjected to four PAR questionnaires to assess physical activity at visits 2, 3, 4 and 5. Subjects showing drastic changes in physical activity will be consulted, monitored, and if necessary, will be eliminated from the study.

To assess changes in dietary restraint, disinhibition and hunger, the Three Factor Eating questionnaire will be administered at both visits 2 and 5. In addition to this, general susceptibility to food cravings will be assessed using the Food Cravings Questionnaire trait administered visits 2 and 5.

Analysis of Whole Body Fat by DXA Scan:

To obtain whole body and segmental changes in body fat and fat free mass including trunk, arms and legs, as well as visceral and subcutaneous fat, two (2) DXA scans will be performed, one at visit 2 and another one at visit 5.

Fasting Resting Metabolic Rate/Respiratory Quotient:

Fasting RMR/RQ will be performed by a member of the study team at visits 2 and 5 to determine fat burning rate.

Electrocardiogram (EKG):

To ensure the safety and suitability of study participants, as well as of the supplement, two separate EKGs will be performed at visits 2 and 3. EKGs will be performed to assess heart activity and any changes that may occur throughout the study.

Vital signs and anthropometric measures:

The following measurements will be completed at selected study visits:

Body weight: screening, visits 2, 3, 4 and 5

Body height: screening, visits 2, 3, 4 and 5

Waist and hip circumferences: visits 2 and 5

Skinfold thickness: visits 2 and 5

Systolic blood pressure: screening, visits 2, 3, 4 and 5

Diastolic blood pressure: screening, visits 2, 3, 4 and 5

Heart rate: screening, visits 2, 3, 4 and 5

Subjects with weight loss of more than 10 lbs between visits will be evaluated by the study MD, and further action will be determined at his discretion.

Compliance:

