Study participants will be contacted by a member of the study team each week either by phone or by email to monitor adherence to the intervention and to monitor self-reported health changes. Study team members will fill out a weekly log to ensure that volunteers have been contacted. If any abnormalities are reported, the study physician will be informed. The study physician will advise the participant to follow up with their primary care physician and also decide if the participant can continue with the intervention.

Participants will receive a compliance calendar used to track their supplement intake at visit 2.

Participants will be required to return any unused supplements and compliance calendar at visits 3, 4 and 5. Participants that miss a visit beyond the allowed interval (4 weeks \pm 1 week from previous visit) will be instructed to discontinue their supplement, if they have not done so already, and they will be removed from the study.

V. Location

This study will be performed at the Metabolic Research Unit and Vascular Biology Laboratory at the Jean Mayer USDA Human Nutrition Research Center on Aging at Tufts University, located at [name].

DXA scans will be performed at the Body Composition Analysis Center at Tufts University Friedman School of Nutrition and Science Policy, located at [name].

VI. Transportation

Volunteers will be required to provide their own transportation to the HNRCA. The building is accessible by public transportation. However, if

participants should choose to drive, they can obtain parking validation at a reduced cost.

VII. Personnel who will conduct the study

a. Present During Study Procedures:

Study Nurse
Study Coordinators
Principal Investigator

b. Primary Responsibility for the Following Activities

i. Obtaining Informed Consent

Authorized MRU staff
Principal Investigator
Study Coordinators

ii. Providing On-Going Information to the Study Sponsor and the IRB

Principal Investigator
Co-Investigator
Study Physician

iii. Maintaining Participant's Research Records

Authorized MRU staff
Principal Investigator
Study Coordinators

VIII. Subject Payment

Screening Stipend: \$25

Visit 1 Stipend: \$50

Visit 2 Stipend: \$150

Visit 3 Stipend: \$50

Visit 4 Stipend: \$50

Visit 5 Stipend: \$305

Subjects will only be paid for each completed visit, and will not be paid if they withdraw or are withdrawn from the study.

IX. Confidentiality

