All stipends will be mailed to participants in the form of checks 2-3 weeks after they complete each visit. Participants who are removed from the study or choose to drop out will be paid for their completed visits only, and will not be paid if they are removed or choose to drop out before the completion of any study visit. In the event of a government shutdown or any other emergency situation, stipend will be delayed until the shutdown or emergency has ended.

F. Specific Procedures Used Throughout this Study

Distribution and Storage of Dietary Supplement

Supplements and placebo will be labeled in a binary (e.g., A or B) fashion without study staff's knowledge of which is which. Both supplement and placebo will be stored in locked cabinets at the MRU. The two will be distributed to participants, in accordance with their randomization scheme, starting at visit 2. Participants will receive an extra week's worth of supplements at each visit wherein supplement is distributed in anticipation of events that may keep volunteers from attending their next visit after 4 weeks.

Weight and Height:

Body weight will be measured during each visit to the HNRCA, aside from visit 1. Participants will be asked to change into scrubs provided by MRU during weight measurement to ensure the most accurate measurement.

Height will be measured at each visit to the HNRCA except enrollment. Shoes and head dressings or ornaments will be removed. Measurements will be taken according to standard procedure.

Waist and Hip Circumference:

Waist and hip circumference will be measured at visits 2 and 5. Measurements will be taken against the skin. Waist circumference will be measured at the approximate midpoint between the lower margin of the last palpable rib and the top of the iliac crest. Hip circumference will be measured around the widest portion of the buttocks with the tape parallel to the floor. These measures will be performed in duplicate and averaged.

Resting Metabolic Rate (RMR):

RMR measures will be performed only at the visits 2 and 5. Subjects will arrive at the HNRCA in a fasted state. Subjects will undergo bed rest for 30 min prior to measurement. Systolic and diastolic blood pressure will be measured. Measures of VO_2 and VCO_2 will be made

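### The SAP's only stated analysis set is completers, which is settled after supplement is dispensed; it gives no all-randomised efficacy set, no all-dosed safety set and no method for missing week-12 DXA

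*SAP*

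**What the plan says.** The Statistical Analysis Plan section of the SAP says "All subjects who completed the study were included in the analysis" and then lists a t-test or Wilcoxon test for continuous variables and a Fisher or chi-square test for categorical ones. It does not define completion. The supplied SAP text is one paragraph, and part of the file was not available, so statements here about what is absent refer to the supplied text.

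The protocol places the events that settle completion after the capsules are handed out:

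- **Dispensing** (III.F, Distribution and Storage): "The two will be distributed to participants, in accordance with their randomization scheme, starting at visit 2".
- **Withdrawal criteria** (III.C): "Low compliance including taking less than 80% of study supplements, or missing study visits", allergic reaction, and "Negative health effects as determined by the study physician".
- **Visit outside the window** (III.E.IV, Compliance): such subjects "will be instructed to discontinue their supplement, if they have not done so already, and they will be removed from the study".
- **Discretionary removal** (III.E.IV, Nutritional Intake and Physical Activity): "Subjects showing drastic changes in physical activity will be consulted, monitored, and if necessary, will be eliminated from the study". III.F, Volunteer Consent and Safety, also allows removal for a severe reaction.
- **Liver signal at visit 3 or 4** (III.E.IV, note under the blood collection scheme): "subjects will be asked to discontinue the supplement and to take medical action at the discretion of the study physician". The note does not say whether the subject leaves the study.

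Body fat is measured twice: "two (2) DXA scans will be performed, one at visit 2 and another one at visit 5". Safety is Specific Aim 2. Under III.G the principal investigator reviews retention and reasons for drop-out and gives the IRB summaries of all adverse events.

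**The concern.** Randomisation protects a comparison of everyone randomised. Here the analysed group is fixed later, by events that the capsule could influence: tolerability, adherence, willingness to attend, and the physician's view of harm. If those events relate to body-fat change differently in the two arms, the completer difference is not the treatment effect. With no DXA between visits 2 and 5, a subject who leaves in between has no follow-up body-fat value, and the supplied text does not say how that gap is handled.

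For safety, withdrawal for harm is a written criterion. Nothing in the SAP separates Aim 2 from its one stated set. If that set is used, a between-arm statement of no ill effect would rest on subjects who were not withdrawn for harm.

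**Working it through.** **1. Reproducing the plan's figures (Protocol III.B).** Inputs: EMIQ 19 (SD 24.62), placebo 1 (SD 12.87), difference d = 18, formula N = 1 + 16S²/d².

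- With S as the mean of the two SDs, 18.745: N = 1 + 16 × 18.745²/18² = 18.4, matching the stated 18.
- With the pooled SD, √((24.62² + 12.87²)/2) = 19.64: N = 20.1.
- Power at 25 per arm with the pooled SD (noncentral t, two-sided 5%) is 88.8%, consistent with the stated figure of more than 85%.
- The planned difference is 18/19.64 = 0.916 SD.

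**2. Allowance for loss.** 64 enrolled for 50 completers is 14/64 = 21.9%. III.E.I instead randomly assigns 50 and, further on, admits 50. The number randomised is therefore unclear, and some or all of the 14 may be lost before randomisation. Nor is 14 a cap.

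**3. Illustrative bias.** Assumptions: no true effect, 25 completers per arm, L selective leavers from EMIQ only whose mean is 0.5 or 1 SD worse than that of EMIQ completers, and placebo losses unrelated to outcome. Bias = L/(25 + L) × gap; type I error is from the noncentral t with 48 df.

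| L | Bias, SD (gap 0.5 / 1) | Type I error (gap 0.5 / 1) |
|---|---|---|
| 1 | 0.019 / 0.038 | 5.1% / 5.2% |
| 3 | 0.054 / 0.107 | 5.4% / 6.6% |
| 7 | 0.109 / 0.219 | 6.7% / 11.8% |

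A simulation (100,000 runs per cell; 1, 3 or 7 leavers per selected arm; leaving score correlated 0.3 or 0.5 with outcome) shows how the direction depends on the pattern. Selection in both arms gives mean bias within 0.002 SD of zero and type I error of 5.1% to 5.8%. Selection in placebo only gives −0.02 to −0.18 SD.

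**4. Tipping point.** Let p = L/(25 + L) and let leavers be worse by a shift δ in SD units. The all-randomised estimate is D − pδ with variance 2/25 + p(1 − p)δ²/(25 + L). The critical t(48) is 2.011, so significance among completers needs 2.011 × √(2/25) = 0.569 SD (11.2 units). Solving for the δ at which significance is lost:

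| Completer difference D | L = 1 | L = 3 | L = 7 |
|---|---|---|---|
| 0.916 SD (planned) | 5.5 SD | 2.55 SD | 1.4 SD |
| 0.60 SD (11.8 units, p = 0.039) | 0.74 SD | 0.28 SD | 0.14 SD |

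**5. Is a subject with a liver signal a completer?** Two capsules a day for 84 days is 168. Stopping at week 4 or week 8 on nominal timing means 56/168 = 33% or 112/168 = 67%, below the 80% in III.C. The liver note does not state removal. Completion status therefore depends on how the two places are read together.

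**6. Power cost of analysing everyone.** Assumption: L EMIQ subjects gain nothing and there are 25 + L per arm. The mean difference is 18 × 25/(25 + L). The lower power figure adds the mixture variance.

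| L | Difference | Power |
|---|---|---|
| 0 | 18.0 | 88.8% |
| 1 | 17.3 | 87.1% to 87.6% |
| 3 | 16.1 | 83.8% to 85.2% |
| 7 | 14.1 | 77.7% to 80.5% |

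**The case against.** The SAP says that completers were included, not that only they were, and it never says how adverse events are analysed. The trial is double-blind and staff do not know which label is which, so removals for activity, attendance or compliance are not knowingly arm-based. If all 14 planned losses fell before randomisation, completers and randomised subjects could be the same people. The larger type I error figures need seven selective leavers in one arm, and the 0.60 SD example is fragile because it lies just above the 0.569 SD threshold.

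All of this limits the size of the problem. It does not remove it: no second set is named, blinding does not stop tolerability or effect from influencing who stays, and the documents do not show that losses precede dispensing.

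A reader might infer four stronger things that the documents do not support:

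- **That harmed subjects are certainly dropped from the safety analysis.** This holds only if the one stated set is applied to Aim 2. Events are still captured and summarised to the IRB; what is missing is a specified comparison by arm. A subject who stops the supplement for a liver signal may also still complete.
- **That the liver note contradicts the withdrawal criteria.** The note can be read as an instance of withdrawal for negative health effects. It is silent on study status, which is an ambiguity.
- **That the bias favours EMIQ.** The direction reverses if the selection is in the placebo arm.
- **That the completer analysis was prespecified.** The supplied SAP text is undated and in the past tense, and the protocol's 50 completers are a sample-size target.

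**Conclusion.** The point stands as a defect in the analysis plan. Followed as written, efficacy is a completer comparison, close to per-protocol, with no stated way to examine the effect of those who left. The same applies to the between-arm safety comparison if the stated set is used for it.

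No size or direction is claimed for the actual bias, and no size at all for safety, because losses and harm withdrawals by arm are not in the documents. The calculations are conditional. One-sided selection of a few subjects does little to the type I error, seven can roughly double it, and balanced selection leaves the mean difference about unbiased. A completer effect of the planned size would survive plausible departures; one just past the significance threshold could be overturned by a small shift in a few leavers. The point should be fixed before conclusions are drawn on either aim, because without withdrawals by arm and reason a reader cannot tell which case applies.

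**What to change.** Changes to the SAP:

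1. State the number randomised per arm, reconciling III.B with the two statements in III.E.I. Define completion, saying whether a subject asked to stop under the liver note stays in the study. Read that note together with III.C; no stopping rule needs to change for this.
2. For efficacy, analyse all randomised subjects as randomised, with a stated method for missing week-12 DXA. One option is multiple imputation from arm, baseline DXA and any visit 3 and 4 weights, which exist only for subjects who reached those visits. Add a missing-not-at-random analysis reporting the shift at which the conclusion changes.
3. Report completers as a sensitivity analysis. If results were known when the SAP was written, show both analyses side by side, disclose when each was specified, and do not call completers prespecified unless a dated record shows it.
4. Define the safety set as everyone who took at least one capsule, using all adverse events and all available visit 3 and 4 laboratory results and EKGs (the interim EKG is at visit 3). Tabulate withdrawals by arm and reason.

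Most of the cost is wording and analysis of data already held. Seeking visit 5 measurements from subjects who stopped is optional and possible only while follow-up is open. It adds visit costs and needs an amendment, because the Compliance section removes subjects with an out-of-window visit from the study. The statistical cost is dilution by non-adherence: power falls from about 89% to about 84% to 88% with 1 to 3 EMIQ non-gainers, or to about 78% to 80% with 7.

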To calculate number of subjects needed per group and provide 80% power at $\alpha=0.05$ we used mean differences and standard deviation (EMIQ: 19 ± 24.62 and Placebo: 1 ± 12.87) of whole abdominal fat loss from an early published study conducted in Japan, where the Japanese volunteers consumed 275mg EMIQ per day for 12 weeks and showed a positive impact of EMIQ on reduction of fat depots. We plugged in data from that study into this formula $N=1+[16(xS^2/d^2)]$ to calculate sample size. Using this formula the number of subjects in each group were calculated to be $n=18$. However, we selected to use 25 subjects per group which increases power of study to $>85\%$. 25 subjects per group is a conservative sample size, which make us to expect a larger difference in the means with a higher dose of EMIQ intake.

The primary objective of this study is to demonstrate reduction of total body fat following 12 weeks of EMIQ intervention. Therefore, we will determine statistically if EMIQ is effective to reduce percent body weight, total abdominal fat, subcutaneous and visceral fat after 12 weeks of intervention compared to baseline values. We plan to compare the two group medians with the Mann-Whitney U test. After reviewing the data at the completion of the study, we can assume normality, then we will compare the two group means with parametric t-test.

C. Subject Characteristics

Inclusion Criteria:

- Male or female age 18-65 years.
- Premenopausal female with regular menstrual cycle or post-menopausal female with cessation of menstrual cycle for a minimum of 6 months.
- BMI in the range of 26.0-37.0_
- Beck Depression Inventory Score less than 20.
- Fluency in spoken or written English.
- Willingness to be randomized to take EMIQ or placebo.
- Must weigh at least 164lbs

Exclusion Criteria:

- Any major illness or condition that may interfere with study outcomes at the discretion of the study physician.
- Diabetes Type I & Type II, or use of any pharmacological treatment for diabetes.
- Use of medications that interfere with energy metabolism
- Receiving hormone therapy growth hormone, testosterone, or estrogen with the exception of hormone contraceptives.
- GI diseases, conditions or medications known to influence GI absorption including active peptic ulcer disease or inflammatory bowel disease such as

- ulcerative colitis, Crohn's disease, celiac disease, chronic diarrhea or constipation.
- Undergone gastric bypass or other bariatric weight loss procedure.

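### The SAP's pooled t-test should be Welch's: the planning SDs differ 1.9-fold, completer arms may be unequal, and the Wilcoxon fallback does not correct for unequal spread

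*SAP*

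**What the plan says.** The SAP (Statistical Analysis Plan) takes everyone who completed the study as the analysis set. For the comparison of arms it states: "Differences between treatment groups were tested using Student's *t*-test". For departures from assumptions it states: "Two-sample Wilcoxon test is used when variables appear to violate distributional assumptions". It says that assumptions were examined in a baseline-adjusted ANCOVA of the 12-week outcome. It names no unequal-variance test and no robust standard error. Results are summarised as mean and SD; no confidence interval is specified.

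The protocol (III.B, Sample Size and Statistical Analyses) puts the rank test first: "We plan to compare the two group medians with the Mann-Whitney U test". It moves to a t-test if normality looks tenable. The same section gives the only variance information in the two documents: "EMIQ: 19 ± 24.62 and Placebo: 1 ± 12.87) of whole abdominal fat loss from an early published study conducted in Japan".

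Randomisation is 1:1, with 64 enrolled so that 50 finish. The protocol plans 25 per group, but neither document says how many completers each arm had.

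**The concern.** Student's t-test assumes one common variance. When variances differ, it is close to its nominal level only if the arms are about the same size. If the more variable arm is the smaller one, the pooled standard error is too small and the test rejects too often. If that arm is the larger one, the test is conservative and loses power.

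The planning SDs point to a much more variable EMIQ arm. The arm sizes are settled after randomisation, by who completes. The protocol also removes participants for low compliance, missed visits and, if necessary, drastic changes in activity. So the direction of any error depends on dropout.

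The fallback does not close the gap. Wilcoxon tests whether the two distributions are identical. It can be read as a comparison of medians only if the distributions have the same shape and spread and differ by a shift, so the protocol's wording is inaccurate when spreads differ.

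**Working it through.** **Inputs.** Means and SDs from protocol III.B: "EMIQ: 19 ± 24.62 and Placebo: 1 ± 12.87". Difference d = 19 − 1 = 18. SD ratio 24.62/12.87 = 1.91; variance ratio 606.14/165.64 = 3.66. Enrolled 64, completers 50, so 14 losses. Alpha is 0.05; the documents do not say one- or two-sided, so two-sided is assumed.

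**Reproducing the plan's sample size.** The formula is given as "We plugged in data from that study into this formula $N=1+[16(xS^2/d^2)]$ to calculate sample size", with a single S.
- S as the simple average, (24.62 + 12.87)/2 = 18.745: N = 1 + 16 × 351.4/324 = 18.35, which matches the stated 18 per group.
- S as the root mean square, √385.89 = 19.64: N = 1 + 16 × 385.89/324 = 20.06.
- Power at 25 per group (noncentral t): 91% with the first S and 89% with the second. Both agree with the stated figure of more than 85%.

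The planning therefore reproduces, and it already compressed two very different SDs into one.

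**Standard errors.** Pooled variance = [(n₁ − 1)s₁² + (n₂ − 1)s₂²]/(n₁ + n₂ − 2). Pooled SE = √[pooled variance × (1/n₁ + 1/n₂)]. True SE = √(s₁²/n₁ + s₂²/n₂).
- 25:25 (EMIQ:placebo): 5.556 against 5.556, ratio 1.00.
- 22:28: pooled variance (21 × 606.14 + 27 × 165.64)/48 = 358.4; SE 5.393 against 5.785, ratio 0.93.
- 28:22: 5.793 against 5.402, ratio 1.07.

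**Type I error by simulation.** Normal data, equal means, the planning SDs, two-sided 5%. There were 400,000 trials per split for Student and Welch, and 200,000 for Wilcoxon (normal approximation with continuity correction). Repeat runs agree to about 0.1 point.

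| EMIQ:placebo | Student | Wilcoxon | Welch |
|---|---|---|---|
| 25:25 | 5.2% | 5.4% | 5.0% |
| 24:26 | 5.7% | 5.9% | 5.0% |
| 26:24 | 4.7% | 5.2% | 5.0% |
| 22:28 | 6.9% | 6.7% | 5.0% |
| 28:22 | 3.7% | 4.7% | 5.0% |
| 20:30 | 8.3% | 7.1% | 5.0% |
| 30:20 | 3.0% | 4.1% | 5.0% |

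**Range over the SD ratio.** The ratio for this trial's own endpoint is not given, so the 22:28 split was rerun with other values. Student's error is 5.0% at a ratio of 1.0, 5.6% at 1.25, 6.2% at 1.5 and 6.9% at 1.91.

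**How likely is a bad split?** Assume 14 losses at random from 32 + 32, so losses from EMIQ are hypergeometric.
- Exactly 25:25: C(32,7)²/C(64,14) = 24%.
- Both arms between 23 and 27: 87%.
- EMIQ arm 22 or fewer: 6.4%. Either arm 22 or fewer: 2 × 6.4% = 13%.
- EMIQ arm 20 or fewer: 0.26%.
- Student's error averaged over all these splits: about 5.2%.

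**The case against.** The case for leaving the plan alone has real force, and most of it stands.

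- **The planned design is balanced.** At 25:25 Student's test is essentially exact despite the SD ratio, and 24:26 moves it by less than one point. A reader might infer that any inequality of arms spoils the 5% level; the table does not support that. A shift of about two points needs roughly 22:28 with EMIQ the smaller arm. Dropout related to arm would make such splits likelier, but neither document reports dropout by arm.
- **The SDs are borrowed.** They describe abdominal fat loss in another population at a lower dose. The stated primary objective here is total body fat, for which no SD is given.
- **The null matters.** The SDs were observed alongside an apparent effect. If EMIQ does nothing to anyone, randomised arms share one distribution and both tests keep their level, selective dropout aside. The mis-sizing needs equal means with unequal spread. That can arise if some participants respond and others do the opposite or do not respond, but it is a premise and not a finding.
- **No interval is planned.** A reader might conclude that the plan's error bars are wrong. The SAP reports each arm's mean and SD, which pooling does not touch. Only an interval built on the pooled SE would be off, by about 7% at 22:28 or 28:22.
- **Wilcoxon's worst case is constructed.** With an assumed skewed distribution (gamma, shape 2, equal means, the planning SDs), Wilcoxon rejects about 12% of the time even at 25:25. Nothing in the documents supports that shape, and since the distributions differ, these are not false rejections of Wilcoxon's own null.
- **Assumptions are checked.** The SAP does look at assumptions in an ANCOVA. But the only response it names is Wilcoxon, which in the table drifts in the same direction as Student, though by less at the more unequal splits.

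**Conclusion.** The point holds as a modest, conditional weakness. The SAP commits to an equal-variance test on a completer set of uncontrolled arm sizes. The sponsor's own planning SDs differ 1.9-fold, and the named fallback is no remedy for that. If that ratio carried over and mean changes were equal, the nominal 5% would be about 7% at 22:28 and about 3% at 30:20. Under random loss, the inflating direction reaches 22:28 or worse only 6.4% of the time.

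The figures rest on normal data, a two-sided test, random loss and a borrowed SD ratio. The documents do not show that the trial's actual error rate was wrong, because they give neither the completer split nor the SDs of the outcome. The reason to act is that the protection is nearly free. The inaccurate description of Mann-Whitney as a comparison of medians under unequal spread needs correcting whatever the split.

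**What to change.** 1. In the SAP, replace Student's t-test with Welch's unequal-variance t-test, and report the difference in mean change with its Welch 95% confidence interval.
2. If a baseline-adjusted model is used for the treatment comparison, specify heteroskedasticity-robust standard errors.
3. Do not use Wilcoxon as the response to unequal variance. If it is kept for skewed variables, keep the mean difference and its interval beside it.
4. In protocol III.B, remove the statement that the Mann-Whitney test compares medians.

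The cost is a few sentences and a software option. At 25:25 with a true difference of 18 and the planning SDs, power is about 88.3% for Welch against 88.7% for Student, a gap of under half a point. At 28:22 Welch gains (90.2% against 87.5%). At 22:28 it appears to lose (85.4% against 89.0%), but there Student's figure comes from a test running at about 7%, so the two are not like for like.
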